7.4.4 Handling of Multiple Assessments in a Specific Time Window

For all parameters except MBL volume, multiple assessments in a specific time window will be handled as follows:

1. For parameters other than BMD, TVU/TAU, MRI, and WPAI data, if more than one assessment is included in a time window, then the assessment performed closest to the scheduled study day (i.e., the nominal day) will be used in the analyses. If more than 1 day is of equal proximity to the nominal day, then the data collected after the nominal day will be used in the analyses.
2. For BMD, TVU/TAU, and MRI data, if multiple assessments exist in a specific time window, analyses of data will be based on the most conservative (worst) assessment.

3. For WPAI data, if multiple assessments exist in a specific time window in the treatment period, analyses of data will be based on the last assessment during the treatment period.

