In the event the Month 6 biopsy cannot be performed (e.g., due to a stenotic cervix or location of fibroids), or an insufficient biopsy sample is obtained and the concurrent TVU indicates a thickness of > 4 mm, a repeat biopsy must be performed. If upon repeat, a sample cannot be obtained or remains insufficient, the AbbVie TA MD should be consulted.

If a repeat biopsy is performed and the results are normal or the sample contains scant endometrium without abnormalities, the subject is eligible to enter the extension study.

Subjects with abnormal endometrial pathology results (including, endometrial hyperplasia with or without atypia and endometrial cancer) at Treatment Month 6 are not eligible to enter the extension study and instead will enter the Post-Treatment Follow-up Period. The endometrial pathology should be managed according to standard of care.

Physical Examination

A complete physical examination will be performed during the Washout Period (if applicable) or Screening Period and will include height and weight measurements (the subject should not wear shoes). Subjects who entered washout will only be required to have a symptom-directed physical examination performed when they enter the Screening Period.

During the Treatment Period and Post-Treatment Follow-Up Periods, a complete physical examination will be performed at Day 1 (prior to dosing), Month 6 and Post-Treatment Follow-up Month 6 or Premature Discontinuation. The complete physical examination at Day 1, Month 6 or Premature Discontinuation will include weight measurements. Symptom Directed Physical Examinations will be performed as specified in Appendix C.

Clinically significant physical examination findings prior to randomization will be recorded as medical history. Any clinically significant physical examination findings after dosing will be recorded in the source documents and in the eCRFs as adverse events.

Vital Signs

Vital sign determination of heart rate, blood pressure, respiratory rate and body temperature will be obtained at all visits during the study as indicated in Appendix C. The blood pressure and heart rate measurements should be taken prior to scheduled blood collections. Body temperature measurements should be assessed using the same modality consistently throughout the study, e.g., oral, aural, axillary, etc., and the modality will be reported in the source documents and eCRF.

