Table 3 and Table 4 will be used for analyses of endpoints collected at Month 6 (biopsy, MRI, BMD) in the Treatment Period.

Table 3. Analysis Time Windows for Non-Bleeding Measurements Collected Every 6 Months in the Treatment Period (BMD)

Visit	Nominal Day (Study Day)	Time Window (Study Days)
Prior to Month 3		>1 – ≤ 84
Between Month 3 and Month 6	84	> 84 – ≤ 140
Month 6	168	> 140 – ≤ 196

Table 4. Analysis Time Windows for Non-Bleeding Measurements Collected Every 6 Months in the Treatment Period (MRI and Biopsy)

Visit	Nominal Day (Study Day)	Time Window (Study Days)
Prior to Month 6	70	> 1 – ≤ 140
Month 6	168	> 140 – ≤ 196

Table 5 will be used for analyses of endpoints collected at Post-Treatment Month 1, 3, 6, 9, and 12 (e.g., vital signs, clinical safety labs including chemistry, hematology, lipid panel and urinalysis, apolipoprotein A and B). Table 6 will be used for analysis of endpoints collected at Post-Treatment Month 3 and 6 (e.g., TAU/TVU). Table 7 will be used for analysis of endpoints collected at Post-Treatment Month 3 (e.g., MRI). Table 8 will be used for analysis of endpoints collected at Post-Treatment Month 6 and 12 (e.g., BMD).

Table 5. Analysis Time Windows for Non-Bleeding Measurements Collected at Post-Treatment Month 1, 3, 6, 9, 12

	Nominal Day (Study End Day)	Time Window (Study End Days)
Post-Treatment Month 1	28	> 3 – ≤ 42
Post-Treatment Month 3	84	> 42 – ≤ 126
Post-Treatment Month 6	168	> 126 – ≤ 210
Post-Treatment Month 9	252	> 210 – ≤ 294
Post-Treatment Month 12	336	> 294

Table 6. Analysis Time Windows for Non-Bleeding Measurements Collected at Post-Treatment Month 3 and 6

	Nominal Day (Study End Day)	Time Window (Study End Days)
Post-Treatment Month 3	84	> 28 – ≤ 126
Post-Treatment Month 6	168	> 126 – ≤ 210
Post-Treatment Months 7 – 12		> 210

Table 7. Analysis Time Windows for Non-Bleeding Measurements Collected at Post-Treatment Month 3

	Nominal Day (Study End Day)	Time Window (Study End Days)
Post-Treatment Month 3	84	> 28 – ≤ 126
Post-Treatment Months 4 – 12		> 126

Table 8. Analysis Time Windows for Non-Bleeding Measurements Collected at Post-Treatment Month 6 and 12

	Nominal Day (Study End Day)	Time Window (Study End Days)
Prior to Post-Treatment Month 6		> 28 – ≤ 140
Post-Treatment Month 6	168	> 140 – ≤ 196
Post-Treatment Months 7 – 11		> 196 – ≤ 308
Post-Treatment Month 12	336	> 308

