12.6 Endometrial Biopsy

The number and percentage of subjects in each category of endometrial biopsy results will be summarized at Baseline, Between Month 3 and Month 6, and Month 6 for each treatment group.

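### When a Month 6 endometrial biopsy is repeated, the SAP can tabulate the insufficient first sample instead of the adequate repeat, because biopsy is left out of the worst-result rule

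*SAP*

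**What the plan says.** SAP 7.4.4 has a default rule and two exceptions for several assessments in one window.

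- The default applies to "For parameters other than BMD, TVU/TAU, MRI, and WPAI data, if more than one assessment is included in a time window". It states that "the assessment performed closest to the scheduled study day (i.e., the nominal day) will be used in the analyses". Ties go to the later sample: "If more than 1 day is of equal proximity to the nominal day, then the data collected after the nominal day will be used".
- The worst-result exception begins "For BMD, TVU/TAU, and MRI data, if multiple assessments exist in a specific time window". Biopsy is not named. The other exception concerns WPAI only.

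SAP 7.4.3 places biopsy in the Month 6 tables: "Table 3 and Table 4 will be used for analyses of endpoints collected at Month 6 (biopsy, MRI, BMD) in the Treatment Period". Table 4, shared by MRI and biopsy, sets nominal Day 168 and a Month 6 window after Day 140 up to Day 196. SAP 7.4.1 names biopsy alongside BMD, ultrasound and MRI when it retains data up to 28 days after the last dose. SAP 7.5 takes the worst of several biopsy results only when they fall on the same day.

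Protocol 5.3.1.1 (Endometrial Biopsy) makes a repeat mandatory if the Month 6 biopsy cannot be done, or if "an insufficient biopsy sample is obtained and the concurrent TVU indicates a thickness of" more than 4 mm. Protocol Table 1 allows the Month 6 biopsy from 15 days before to 4 days after the visit, and the text recommends about 15 days before.

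The planned analysis in SAP 12.6 is one sentence: "The number and percentage of subjects in each category of endometrial biopsy results will be summarized". It names three time points: Baseline, the interval from Month 3 to Month 6, and Month 6.

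**The concern.** A repeat biopsy is taken because the first sample gave no diagnosis in a woman whose endometrium is not thin. Choosing between the two by calendar distance ignores which one carries information. The Month 6 table can then show her as insufficient when an adequate repeat, possibly showing hyperplasia, is in the database.

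The omission looks unintended. Biopsy is grouped with BMD, ultrasound and MRI for the 28-day cut-off and shares MRI's window, yet it is separated from them for repeat assessments without a stated reason. Two samples on one day are resolved by the worst result; two samples a week apart are not.

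Biopsy findings are a listed safety variable (protocol 5.3.5), and biopsy results are a surveillance source for endometrial safety in SAP Appendix Q. Abnormal results are expected to be rare, so a single one matters to how the table reads.

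**Working it through.** The plan states no figure on this point, so there is nothing to reproduce. The check applies the selection rule to possible pairs of days.

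**Inputs.** Nominal day 6 × 28 = 168; window Days 141 to 196 (SAP Table 4). First-biopsy days 168 − 15 = 153 to 168 + 4 = 172 (protocol Table 1, taking the visit at Day 168), which is 20 possible days. The gap between first biopsy and repeat is not in the documents; 7 to 28 days is an assumption. An insufficient sample is taken to count as an assessment.

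**Rule.** Let the first biopsy be on day d and the repeat on a later day r.

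- If d ≥ 168, then r − 168 > d − 168, so the first is always kept.
- If d < 168 and r is after Day 168, the repeat is kept when r − 168 ≤ 168 − d, that is r ≤ 336 − d (a tie goes to the repeat).
- If both fall before Day 168, the repeat is nearer and is kept.

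**Examples.**

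- d = 153: repeat kept through 336 − 153 = Day 183; first kept from Day 184.
- d = 160: repeat kept through Day 176; first kept from Day 177.
- d = 162, r = 176: distances 6 and 8, first kept.
- d = 168, r = 182: distances 0 and 14, first kept.

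**Across the allowed window.** With gap g, the first is kept when d > 168 − g/2.

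| Assumed gap (days) | First kept if taken on | Days out of 20 |
|---|---|---|
| 7 | 165–172 | 8 |
| 14 | 162–172 | 11 |
| 21 | 158–172 | 15 |
| 28 | 155–172 | 18 |

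These are counts of days, not probabilities; the recommended timing favours the early days. In 4 of the 18 days in the last row (169–172) the repeat falls on Days 197–200, outside the window.

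**After Day 196.** Protocol 5.4.4 keeps women on drug until extension eligibility is settled, and SAP 10.0 has an exposure category above 196 days. A repeat then passes the SAP 7.4.1 cut-off but has no Table 4 window. SAP 12.6 has no Final Visit column, worst-result summary or listing to catch it. For BMD, SAP 12.4.1 has a Final Visit summary, worst-score summaries and listings.

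**Size.** Exact two-sided 95% upper limits, taking all 200 women in the E2/NETA arm as biopsied (a ceiling, since no biopsy is required after discontinuation before Month 3):

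- 0/200: 1 − 0.025^(1/200) = 1.83%.
- 1/200 = 0.5%: upper limit about 2.75%.

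The documents give no insufficient-sample rate. At an assumed 5–15%, 200 × 0.05 = 10 to 200 × 0.15 = 30 women would have an insufficient first sample. Taking 1.8% as the hyperplasia rate gives 10 × 0.018 = 0.18 to 30 × 0.018 = 0.54 cases, before requiring thickness above 4 mm, a completed repeat and adverse timing.

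**The case against.** The strongest reply is that an insufficient sample has no diagnosis and might be handled as missing. SAP 12.1 leaves women with a missing evaluation out of that visit, and SAP 12.6 does not name its categories. An in-window repeat would then be used every time. This is a fair reading, but the SAP does not state it, and the protocol (Central Imaging Procedures, and the Appendix C footnote) speaks of insufficiency as a biopsy result. Nor would it help a repeat after Day 196.

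The second reply is timing. A first biopsy at about Day 153 leaves 30 days for a repeat that will still be selected. That stands and reduces the frequency, but early timing is a recommendation and later days are allowed.

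Third, other reporting is not governed by SAP 7.4.4. Appendix Q also uses two SMQs for endometrial safety, adverse events follow the 30-day treatment-emergent rule, and abnormal pathology bars entry to the extension, with reasons for non-enrolment summarised by arm. This also stands. A reader might infer that documented hyperplasia would vanish from the safety record; the documents do not support that.

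A reader might also infer that an abnormal first sample could be replaced by a later normal one. The selection rule would permit it, but no scheduled path leads there. The mandatory repeat is for absent or insufficient samples; women with abnormal Month 6 pathology enter follow-up under standard of care, and the follow-up schedule has no biopsy.

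**Conclusion.** The point holds as a gap in the SAP's selection rule and should be closed before the end-of-treatment analysis. As written, a non-diagnostic Month 6 sample can displace an adequate repeat: always if the first is on Day 168 or later, and for earlier first biopsies when the repeat falls after Day 336 − d. A repeat after Day 196 is not tabulated at all.

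The displacement rests on one assumption, that an insufficient sample counts as an assessment. The Day 196 gap does not depend on it.

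The consequence is limited to the Month 6 biopsy category table. The 10 to 30 women computed above should not be read as the number misreported: they are all insufficient first samples at an assumed rate, and even a generous calculation gives fewer than one expected displaced case. The reason to act is that one case separates none observed from some observed, and the correction is cheap.

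**What to change.** In SAP 7.4.4, add endometrial biopsy to the worst-assessment rule and state the ranking of diagnostic categories that defines worst. State that an insufficient or not-performed biopsy counts only if the window contains no adequate sample. In SAP 12.6, add a summary or listing of the worst adequate on-treatment biopsy through 28 days after the last dose, the limit already in SAP 7.4.1, so that repeats after Day 196 are reported.

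Two related texts need reconciling. SAP 12.6 reports a Between Month 3 and Month 6 column, while Table 4 defines Prior to Month 6 for biopsy. Protocol 5.3.1.1 gives the thickness trigger for a repeat as above 4 mm in one subsection and as 4 mm or more in another.

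The cost is a few lines of text and minor programming, with no new procedure and no effect on efficacy or alpha. The reported abnormality rate may move slightly in either direction: adequate repeats can add abnormal findings, while normal late results enlarge the denominator.

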Clinical safety laboratory tests consist of hematology, clinical chemistry, including lipid panel and urinalysis samples. The clinical chemistry and lipid panel samples should be obtained in the morning following an overnight fast (minimum of 8 hours); however,

there may be circumstances when a sample is obtained later in the day and/or not under fasting conditions. If a sample was obtained with less than 8 hours of fasting, the Source Documents and the lab requisition should be marked to indicate that the sample was obtained under non-fasting conditions.

Lipid Panel

If, during the Treatment or through Post-Treatment Period Month 12 Visit the lipid panel results for LDL cholesterol, Triglycerides, Total cholesterol are more than $3 \times$ the upper limit of normal range and the sample was not obtained under fasting conditions (minimum 8 hour fast), the subject will return to the office as soon as possible to have the panel repeated under fasting conditions.

Apolipoprotein A and B, (Apo A and Apo B)

Blood samples for Apo A and Apo B will be collected as part of the chemistry panel. The Apo A and Apo B data are exploratory and results will not be provided to the investigative site.

Serology Testing for Hepatitis and HIV

Subjects will be tested for HAV-IgM, HBsAg, HCV Ab HIV and anti-HIV Ab by the central laboratory during the Screening Period. If any of these tests are positive or reactive, the subject is excluded from study participation. Borderline hepatitis test results should be repeated.

HIV testing will be conducted by ELISA; if the test result is reactive, testing will automatically reflex to Multispot assay. If results are negative or indeterminate, HIV-1 TMA assay is performed to complete the confirmation with results of: Not Detected or Detected. If the HIV ELISA test result is reactive or TMA assay results are detected, the subject will be screen-failed.

The results of the HIV and anti-HIV Ab testing will be retained confidentially by the study site.

Urine Test for Gonorrhea and Chlamydia (Optional)

Gonorrhea and chlamydia testing can be ordered at the Investigator's discretion during the Screening Period, to test for active gonorrhea or chlamydia prior to undergoing the endometrial biopsy and SIS. Any treatment provided will occur outside of the protocol.

Endocrine Panel

The endocrine panel consists of the following analytes: FSH, LH, reflexive TSH and thyroxine-binding globulin (TBG).

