- TG: ≤ 150 , $> 150 - \leq 300$, $> 300 - \leq 500$, $> 500 - \leq 1000$, and > 1000 mg/dL
- LDL-C/HDL-C ratio: ≤ 3 , and > 3
- Total cholesterol/HDL-C ratio: ≤ 4.5 , and > 4.5 .

In addition, the number and percentage of subjects who have potentially clinically significant (PCS) lipid values meeting the following criteria any time during the Treatment Period will be summarized by treatment group:

- Total cholesterol > 200 mg/dL
- LDL-C > 130 mg/dL
- LDL-C > 160 mg/dL
- HDL-C < 40 mg/dL
- TG > 150 mg/dL
- TG/HDL-C ratio > 3.5
- LDL-C/HDL-C ratio > 4 .

Plots will be provided by treatment group for HDL-C, LDL-C, triglycerides, and hemoglobin during the Treatment Period:

- Final post-baseline lab values vs. Baseline lab values;

- Final post-baseline lab values vs. Baseline lab values for subjects with NCI CTCAE Grade 3 or 4;
- Maximum post-baseline lab values vs. Baseline lab values;
- Maximum

Plots will be provided by treatment group for HDL-C, LDL-C, and triglycerides during the Treatment Period:

- Mean percent change from Baseline in lipid over month.

Post-Treatment Follow-Up Period

Laboratory data collected more than 3 days after the last dose of study drug in the Treatment Period will be included in the summary of data from the Post-Treatment Follow-up Period. Baseline for summaries/analyses in the Post-Treatment Follow-up Period is the same as Baseline for summaries/analyses in the Treatment Period.

In the Post-Treatment Follow-up Period, the following summaries will be presented by treatment group:

- During the Post-Treatment Follow-up Period, shift tables for change from Baseline to relevant Post-Treatment Follow-up visit(s) according to the normal ranges will be provided for LDL-C, HDL-C, TG, and total cholesterol.
- During the Post-Treatment Follow-up Period, shift tables for change from Baseline to relevant Post-Treatment Follow-up visit(s) will also be presented based on the CTCAE grades for LDL-C, HDL-C, TG, and total cholesterol.
- Change in liver enzymes (SGPT/ALT, SGOT/AST, total bilirubin, and alkaline phosphatase) and lipid parameters (LDL-C, HDL-C, TG, and total cholesterol) from Baseline to relevant Post-Treatment Follow-up visit(s) will be summarized by treatment group with descriptive statistics.

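### When the protocol requires a fasting repeat of a lipid panel, the SAP's date-only selection rule can keep the non-fasting value in the by-visit lipid summaries

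*SAP*

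**What the plan says.** **Protocol 5.3.1.1 (Safety Laboratory Tests; Lipid Panel).** Chemistry and lipid samples should be taken in the morning after a fast of at least 8 hours. The protocol accepts that this will not always happen: "there may be circumstances when a sample is obtained later in the day and/or not under fasting conditions". In that case "the Source Documents and the lab requisition should be marked to indicate that the sample was obtained under non-fasting conditions". If LDL-C, triglycerides or total cholesterol exceed 3 × ULN and the sample was non-fasting, "the subject will return to the office as soon as possible to have the panel repeated under fasting conditions". No maximum delay is given for the repeat.

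**SAP 7.4.4.** For all parameters other than MBL volume, BMD, ultrasound, MRI and WPAI, when a window holds more than one value, "the assessment performed closest to the scheduled study day (i.e., the nominal day) will be used in the analyses". The tie rule is: "If more than 1 day is of equal proximity to the nominal day, then the data collected after the nominal day will be used". Lipids fall under this general rule.

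**SAP 7.4.1 and 7.4.3.** Laboratory values more than 3 days after last dose leave the Treatment Period, and this cut is applied before windows are assigned.

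**SAP 12.3.1.** Lipids are analysed as change and percent change by visit, as categories by visit, as shift tables to the minimum, maximum and final value, and as counts of women with "potentially clinically significant (PCS) lipid values meeting the following criteria any time during the Treatment Period". The SAP mentions fasting status in none of these places.

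**The concern.** The protocol does not let a markedly raised non-fasting lipid result stand on its own; it orders a repeat under the intended conditions. The SAP then selects between the two results by calendar distance alone. The repeat necessarily comes after the original, so a rule that favours the day nearest the nominal visit tends to favour the original.

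Lipid change is a safety outcome of real interest here. Protocol 3.2.2 lists changes in serum lipids among the adverse events of special interest and describes dose-dependent lipid increases with elagolix. SAP Appendix Q also lists lipid abnormalities. At stake is whether the by-visit change, percent-change and category tables show the value that the protocol sought to confirm or the value that prompted the repeat. The SAP does take measurement conditions into account elsewhere: in 12.4.1 it repeats the BMD analysis excluding women whose scanner manufacturer changed. Lipids have no comparable provision.

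**Working it through.** The plan states no figure on this point, so there is none to reproduce. The check applies the SAP rules to the dates that the protocol allows.

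**Inputs**
- Nominal days for Months 1 to 5: 28, 56, 84, 112 and 140. Each window runs 14 days past nominal (SAP 7.4.3, Table 1).
- Allowed visit days for Months 1 to 5: nominal ± 4 days. For Month 6: −4 or +6 days (Protocol 5.1, Table 1).
- Delay *k* from the non-fasting sample to the fasting repeat: an assumption, because the protocol says only that it should be prompt. Ranges of 1–3, 1–7 and 1–10 days were tried.

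**Rule.** Let *d* be the visit day minus the nominal day. The non-fasting value lies |*d*| days from nominal and the repeat lies |*d* + *k*| days from it. The non-fasting value is kept when |*d*| < |*d* + *k*|. A tie goes to the later value, which is the repeat.

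**Months 1 to 5, visit on or after nominal (*d* = 0 to +4).** Then *d* + *k* > *d* for every *k* ≥ 1, so the non-fasting value is always kept. Month 3 example: non-fasting on Day 84 (distance 0), repeat on Day 87 (distance 3); Day 84 is analysed.

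**Months 1 to 5, early visit (*d* = −*a*).** The non-fasting value is kept only if *k* > 2*a*:
- *a* = 1: *k* ≥ 3
- *a* = 2: *k* ≥ 5
- *a* = 3: *k* ≥ 7
- *a* = 4: *k* ≥ 9

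Otherwise the repeat is used. Example: non-fasting on Day 82 (distance 2), repeat on Day 85 (distance 1); Day 85 is analysed.

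**Share of date combinations.** There are 9 visit offsets, and the result is the same in each of the 5 months:
- Repeat 1–3 days later: (5×3 + 1) = 16 of 27 per month; 80/135 = 59%.
- Repeat 1–7 days later: (5×7 + 5 + 3 + 1) = 44 of 63 per month; 220/315 = 70%.
- Repeat 1–10 days later: (5×10 + 8 + 6 + 4 + 2) = 70 of 90 per month; 350/450 = 78%.

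These weight every date combination equally. They describe how the rule behaves and do not predict rates in patients.

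**Month 6, assuming last dose on the visit date.** A repeat at *k* > 3 is removed by SAP 7.4.1 before 7.4.4 applies. For *k* = 1 to 3, a visit on or after Day 168 keeps the non-fasting value. A visit 1 day early keeps it only at *k* = 3, and a visit 2 to 4 days early uses the repeat. If dosing continues, for example during a delayed rollover, the 7.4.1 cut does not remove the repeat on that timetable.

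**Tables that do not depend on selection.** The maximum-value shift tables and the any-time counts (which include triglycerides > 150 mg/dL and a TG/HDL-C ratio > 3.5) draw on all Treatment Period values. A later fasting repeat therefore does not displace the non-fasting one. The final-value tables use the last non-missing value within 3 days of last dose, so an eligible repeat that is the last value is used there.

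**The case against.** The strongest reply is that this is narrow and that the SAP's approach is defensible. A required repeat arises only above 3 × ULN on a non-fasting sample; any other non-fasting value has no required repeat for SAP 7.4.4 to override. Early visits with a prompt repeat already yield the fasting value. The protocol words fasting as a recommendation and never calls a non-fasting result invalid. SAP 12.1 analyses observed safety data, and SAP 7.5 deliberately considers all same-day values for shifts and potentially significant values. Removing every non-fasting lipid from the main tables would discard high safety values, including total cholesterol and LDL-C. All of this stands. It limits the remedy, but it does not explain why the value that triggered the repeat should outrank the repeat in a by-visit summary.

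A reader might go further and infer that the triglyceride results are wrong, or that mean percent change is inflated by a calculable amount. The documents support neither. They give no frequency of non-fasting samples and no size of the fasting effect. The Day 1 baseline is open to the same non-fasting allowance, which offsets part of any shift, and a shift common to all arms cancels in the mean difference from placebo.

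A reader might also take the share of women with any non-fasting sample as the share miscounted. Appendix C of the protocol schedules six post-baseline treatment panels (Months 1 to 6). On an assumed non-fasting rate of 5% to 15% per sample, independent across visits, 1 − 0.95⁶ = 26% to 1 − 0.85⁶ = 62% of women would have at least one. That counts exposure to a non-fasting sample; it does not count false abnormal findings.

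**Conclusion.** The point holds in a limited form. By its own terms, the rule in SAP 7.4.4 keeps a non-fasting lipid value over the later, protocol-required fasting repeat whenever a Month 1 to 5 visit falls on or after the nominal day, and for early visits whose repeat is slow. At Month 6 the repeat may instead be lost to the 3-day cut in SAP 7.4.1. This follows from the stated rules; only the repeat delay, and the last-dose date at Month 6, are assumed.

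The consequence is confined to lipid safety summaries. The primary endpoint, the ranked secondary endpoints and the sample size are untouched. Competing pairs are probably few, because the repeat is required only above 3 × ULN. The effect on any lipid estimate or count cannot be computed from the documents. It is worth correcting because the correction is cheap and the present rule selects the less suitable of two available values.

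**What to change.** **SAP 7.4.4.** State that, for lipid-panel parameters, a fasting repeat in the same window replaces the non-fasting original in the by-visit change, percent-change and category analyses. Among in-window pairs, the non-fasting value would then be kept in none of the combinations worked above.

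**SAP 12.3.1.** Keep the all-values tables of potentially clinically significant results and shifts. Add a fasting-samples-only sensitivity version of the lipid change, potentially-clinically-significant and CTCAE-shift summaries, and list the non-fasting values.

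**Cost.** A little extra programming, and a few values lost from the sensitivity tables. One item needs confirming first: the protocol places the non-fasting mark in source documents and on the laboratory requisition but does not state that it reaches the analysis dataset. Visits, procedures and sample size do not change.
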